a Applicable to all patients at time of screening See EC [9] in protocol for treatments that will require washout.

b The maximal baricitinib dose for patients with renal impairment (defined as eGFR <60 mL/min/1.73 m^2) will be 2-mg QD (see Protocol).

- c At Week 36 patients in the placebo treatment arm who have NOT achieved SALT  $\leq 20$  will be rescued and re-randomized in a 1:1 ratio to baricitinib 2-mg or baricitinib 4-mg. All patients in the baricitinib treatment arms will continue in their current treatment arm regardless of treatment response at Week 36. Patients in the placebo arm who have achieved a SALT  $\leq 20$  will remain on placebo at Week 36. These patients who have experienced spontaneous regrowth on the scalp will remain on placebo for the remainder of the trial, even if relapse is observed later during the study.
- d At Week 52, responders (SALT  $\leq 20$ ) who are eligible (i.e., stayed on the same dose of baricitinib from initial randomization at Visit 2) will be randomized in a 3:1 ratio to either stay on their current dose of baricitinib or transition to placebo (randomized withdrawal).
- e Patients who have been in the baricitinib 4-mg treatment group from Baseline and who have never achieved a SALT  $\leq 20$  by Week 52 AND do not have a  $\geq 2$  point improvement in ClinRO Measure for Eyebrow or Eyelash Hair Loss (nonresponders) at Week 52 will be automatically transitioned to placebo. See footnote “f” for discontinuation criteria at Week 76.
- f Patients who are nonresponders (a SALT  $> 20$ ) at Weeks 52 AND 76 will be automatically discontinued from the study at Week 76, unless they have a  $\geq 2$ -point improvement from baseline in ClinRO Measure for Eyebrow or Eyelash Hair Loss. See Protocol for more details.
- g Responders who experience a loss of treatment benefit after Week 52 ( $> 20$ -point absolute worsening in SALT score) who were randomized to placebo at Week 52 (randomized withdrawal) will be retreated with their baricitinib dose, as randomized at Baseline (Visit 2). Patients who were randomized to remain on baricitinib (randomized withdrawal) will continue to receive the same dose of baricitinib. See Protocol for more details.

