Patients who achieve a SALT  $\leq 20$  at Week 52 (responders) AND who have remained on the same dose of baricitinib from randomization (Visit 2) to Week 52, will enter the randomized withdrawal, which is meant to evaluate the change in clinical response after treatment withdrawal, and does not account for whether the sample size is sufficient to detect statistical difference between baricitinib and placebo. It is expected that there would be approximately 100 patients eligible for the randomized withdrawal.

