Uptitration Population	All patients who are randomized to baricitinib 2-mg at baseline having SALT score >20 at Week 52 and were rescued to baricitinib 4-mg dose at Week 52. All patients need to take at least one dose of treatment and have non-missing SALT score on or after Week 52.
Retreated Population	A subset of patients who enter randomized withdrawal (randomized to placebo at Week 52) and were retreated with their baseline baricitinib dose at any time after experiencing loss of treatment benefit (SALT>20).
Safety Population	The safety population is defined as all randomized patients who receive at least 1 dose of investigational product (IP) and who did not discontinue from the study for the reason 'Lost to Follow-up' at the first postbaseline visit. Patients will be analyzed according to the IP to which they were assigned.

Abbreviations: AGA = androgenetic alopecia; GCP = good clinical practice; IP = investigational product.

a Some male patients with Grade IV AGA and female patients with patterned baldness may only be identified after hair regrowth on the scalp.

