### 4.4. Handling of Dropouts or Missing Data

Depending on the estimand being addressed, different methods will be used to handle missing data as a result of intercurrent events. Intercurrent events can occur through but not limited to the following:

- application of one of the censoring rules (including after permanent study drug discontinuation, after rescue therapy, after dose change, or retreatment)
- discontinuation of inadvertently enrolled patients
- discontinuation from the study due to enrollment in other trials, medical, safety or regulatory reasons, investigator decision, and patient decision
- missing an intermediate visit prior to discontinuation, rescue, dose change, or retreatment
- loss to follow-up.

Non-censor intercurrent events are events that are not due to the application of any censoring rule, i.e., the last four items in the list above.

Note that as efficacy and health outcome data can accrue after a patient permanently discontinues study drug or begins rescue therapy or retreatment, specific censoring rules to the data will be applied to all efficacy and health outcome observations subsequent to these events depending on the estimand being addressed. These specific censoring rules are described below.

*The primary censoring rule* will censor efficacy and health outcome results after permanent study drug discontinuation or results that were collected during remote visits due to the COVID-19 pandemic. Therefore, the data collected remotely will be considered “missing”. This censoring rule will generally be applied to all efficacy and health outcome endpoints and conducted for all defined efficacy analysis populations in the Phase 3 portion except for the Randomized Withdrawal Population (defined in Section 4.2.1).

*A secondary censoring rule* will censor efficacy and health outcome results after permanent study drug discontinuation. This censoring rule will not exclude the data collected during remote visits due to the COVID-19 pandemic and will be applied to selected efficacy and health outcome endpoints conducted for the FAS population (defined in Section 4.2.1). This censoring rule will be applied to uptitration population.

*A tertiary censoring rule* will censor efficacy and health outcome results after permanent study drug discontinuation or after retreatment. This censoring rule will be applied to the Randomized Withdrawal Population (defined in Section 4.2.1).

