Severity of Alopecia Tool (SALT)	The SALT uses a visual aid showing the division of the scalp hair into 4 areas with the top of the head constituting 40% of total surface, the posterior/back of head 24%, right side and left side of head 18% each. The percentage of hair loss in each area is determined and is multiplied by the percentage of scalp covered by that area. The total sum of the 4 products of each area will give the SALT score, as developed by the National Alopecia Areata Foundation Working Committee (Olsen et al. 2004). Only terminal hair is included in the SALT; vellus hair or any fine downy hair is not taken into account in the SALT scoring process (Olsen et al. 1999, 2004). The SALT score will range from 0% to	SALT score	Derive the SALT score as follows:  SALT=percentage of hair loss on the top of scalp*40% + percentage of hair loss on the posterior/back of scalp*24% + percentage of hair loss on the left side of scalp*18% + percentage of hair loss on the right side of scalp*18%. SALT will be rounded to a whole number before deriving any subsequent variables.	N/A – partial assessments cannot be saved.
		
 
Change from Baseline in SALT
 
	Change from Baseline: observed SALT score – Baseline SALT	Missing if Baseline or observed value is

Measure	Description	Variable	Derivation/Comment	Imputation Approach if with Missing Components
100%.		score	score.	missing
		▪ Percent change from Baseline in SALT score	% change from Baseline: $100 \times \frac{\text{Observed score} - \text{Baseline}}{\text{Baseline}}$	
		SALT 20	Improvement in Baseline $\geq 20\%$ % change from Baseline $\leq -20$	Missing if Baseline or observed value is missing
		SALT 30	Improvement in Baseline $\geq 30\%$ % change from Baseline $\leq -30$	Missing if Baseline or observed value is missing
		SALT 40	Improvement in Baseline $\geq 40\%$ % change from Baseline $\leq -40$	Missing if Baseline or observed value is missing
		SALT 50	Improvement in Baseline $\geq 50\%$ % change from Baseline $\leq -50$	Missing if Baseline or observed value is missing
		SALT 75	Improvement in Baseline $\geq 75\%$ % change from Baseline $\leq -75$	Missing if Baseline or observed value is missing
		SALT 90	Improvement in Baseline $\geq 90\%$ % change from Baseline $\leq -90$	Missing if Baseline or observed value is missing

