		SALT 100	Improvement in Baseline =100% % change from Baseline = -100	Missing if Baseline or observed value is missing

Measure	Description	Variable	Derivation/Comment	Imputation Approach if with Missing Components
		$SALT \leq 20$	Observed SALT score $\leq 20$	Missing if observed value is missing
		Absolute SALT score $\leq 10$	Observed SALT score $\leq 10$	Missing if observed value is missing
		Time to achieve $SALT \leq 20$	Date of visit for first time achieving $SALT \leq 20$ – randomization date at Visit 2	Censored at the last SALT collection date, scheduled visit date or ETV date during the blind treatment period, whichever is the latest and applicable
		With loss of treatment benefit in SALT from Week 52	Observed SALT score post Week 52 visit – observed SALT score at Week 52 $> 20$	Missing if any of these two observed values is missing.
		Without loss of treatment benefit in SALT from Week 52	Observed SALT score post Week 52 visit – observed SALT score at Week 52 $\leq 20$	Missing if any of these two observed values is missing.
Patient-Reported Outcome (PRO) for Scalp Hair Assessment	It's a novel patient-reported outcome (PRO) assessment of the patient's current extent of scalp involvement. Like the AA-IGA, it is comprised of 5 category response options: 0 = No missing hair (0% of my scalp is missing	PRO for Scalp Hair Assessment score	Single item. Range: 0 to 4	Single items, missing if missing.
		PRO for Scalp Hair Assessment score of 0 or 1	Observed score of 0 or 1	Single items, missing if missing.

Measure	Description	Variable	Derivation/Comment	Imputation Approach if with Missing Components
	hair; I have a full head of hair); 1 = A limited area (1%-20% of my scalp is missing hair); 2 = A moderate area (21%-49% of my scalp is missing hair); 3 = A large area (50%-94% of my scalp is missing hair); and 4 = Nearly all or all (95%-100% of my scalp is missing hair).	PRO for Scalp Hair Assessment score of 0 or 1 with a $\geq 2$ -point improvement from baseline	Observed score of 0 or 1 and change from baseline $\leq -2$	Missing if Baseline or observed value is missing.

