**Table JAHO.4.11 Description of Primary, Secondary and Exploratory Efficacy Analyses**

Measure	Variable	Analysis Method (Section 4.2.3)	Censoring Rule	Population (Section 4.2.1)	Time Point
	Time to achieve SALT $\leq 20$	
 
Descriptive
 
Kaplan-Meier plot
 
	Secondary Censoring Rule	Retreated Population	Week 52 - 200
	Time to loss of treatment benefit (>20-point absolute worsening in SALT score)	
 
Descriptive
 
Kaplan-Meier plot
 
	Tertiary Censoring Rule	Randomized Withdrawal Population	Week 52 - 200
	Proportion of patients achieving an absolute SALT $\leq 10$	Descriptive using Obs and mLOCF	Tertiary Censoring Rule	Randomized Withdrawal Population	Weeks 52-200
		Descriptive using Obs and mLOCF	Secondary Censoring Rule	Uptitration Population	Weeks 52-200
		Descriptive using Obs	Secondary Censoring Rule	Retreated Population	Weeks 52-200
	Proportion of patients with loss of benefit in SALT	Descriptive using Obs and mLOCF	Tertiary Censoring Rule	Randomized Withdrawal Population	Weeks 52-200
	Proportion of patients without loss of benefit in SALT	Descriptive using Obs and mLOCF	Tertiary Censoring Rule	Randomized Withdrawal Population	Weeks 52-200

Measure	Variable	Analysis Method (Section 4.2.3)	Censoring Rule	Population (Section 4.2.1)	Time Point
	SALT Change and Percent Change from baseline	Descriptive using Obs and mLOCF	Tertiary Censoring Rule	Randomized Withdrawal Population	Weeks 52-200
		Descriptive using Obs and mLOCF	Secondary Censoring Rule	Uptitration Population	Weeks 52-200

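### The SAP defines loss of treatment benefit as SALT above 20 in the Retreated Population and as a worsening of more than 20 SALT points everywhere else; use one definition and count retreatment as loss

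*SAP*

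**What the plan says.** In SAP Table JAHO.4.1 the Retreated Population is a subset of the patients randomized to placebo at Week 52, namely those who "were retreated with their baseline baricitinib dose at any time after experiencing loss of treatment benefit (SALT>20". The benefit criterion there is an absolute SALT level.

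Elsewhere the SAP uses a change in SALT:

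- **Section 3.1.2, footnote g to Figure JAHO.3.2** gives the retreatment rule. Responders with more than 20 points of "absolute worsening in SALT score) who were randomized to placebo at Week 52 (randomized withdrawal) will be retreated with their baricitinib dose" given at baseline.
- **Table JAHO.4.6** derives loss as "Observed SALT score post Week 52 visit – observed SALT score at Week 52" exceeding 20.
- **Table JAHO.4.11** lists "Time to loss of treatment benefit (>20-point absolute worsening in SALT score" among the final-lock analyses. Tables JAHO.2.1, JAHO.4.8 and JAHO4.9 also use the worsening definition.

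The tertiary censoring rule in section 4.4 "will censor efficacy and health outcome results after permanent study drug discontinuation or after retreatment". Table JAHO.4.11 applies it in the Randomized Withdrawal Population to time to loss and to the proportions with and without loss. Both proportions are to be shown on observed data and with mLOCF.

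**The concern.** One term has two definitions, and they are not equivalent in this population. A patient who goes from 15 at Week 52 to 25 has lost benefit by the Table JAHO.4.1 wording but has worsened by only 10 points. Section 1 of the SAP records that the Retreated Population definition was modified for Version 5, so the entry was worked on for this version.

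The definition matters because retreatment ends a placebo patient's contribution under tertiary censoring. If retreatment followed the absolute level, some placebo patients could return to drug and be censored before they could show the event that the analysis counts. Kaplan-Meier would treat them as censored, and mLOCF would carry a sub-threshold score forward as no loss. Both would make placebo look better than it was. A programmer who flagged or dated loss from Table JAHO.4.1 would also place it earlier than Table JAHO.4.6 does.

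**Working it through.** **Inputs**

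- Week 52 SALT, s: 0 to 20. Section 4.1 limits the randomized withdrawal to patients with SALT of 20 or less at Week 52.
- Scores are whole numbers: "SALT will be rounded to a whole number before deriving any subsequent variables" (Table JAHO.4.6).
- Rule A (footnote g, Table JAHO.4.6): later SALT t satisfies t − s > 20, so the lowest qualifying score is t = s + 21.
- Rule B (Table JAHO.4.1): t > 20, so the lowest qualifying score is t = 21.

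The plan gives no figure of its own to reproduce.

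**Step 1: distance between the thresholds.** (s + 21) − 21 = s.

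| Week 52 SALT | Rule A met from | Rule B met from | Gap |
|---|---|---|---|
| 0 | 21 | 21 | 0 |
| 10 | 31 | 21 | 10 |
| 15 | 36 | 21 | 15 |
| 20 | 41 | 21 | 20 |

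At s = 20, rule B is met after 1 point of worsening and rule A after 21.

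**Step 2: does one rule imply the other?** Since s ≥ 0, t − s > 20 gives t > 20, so A always implies B. The converse fails for t from 21 to s + 20, which is s values for each s. Summed over s = 0 to 20 that is 20 × 21 / 2 = 210 score pairs meeting B but not A, against 0 meeting A but not B. These are counts of possible pairs, not probabilities.

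**Step 3: consequence if footnote g was followed.** Every retreated patient meets both rules, so the Retreated Population is the same set. The triggering score comes before retreatment, so the event is recorded before censoring and time to loss is unchanged. mLOCF carries the triggering score forward as loss.

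**Step 4: consequence if SALT above 20 was applied.** Patients with s from 1 to 20 reach the trigger s points sooner. Those retreated at a score between 21 and s + 20 are censored without the event.

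**Step 5: observed-data proportions under either rule.** At a later visit, let n be the placebo patients still observed and not retreated, L those of them showing loss, and k those retreated earlier. Tertiary censoring removes the k patients from both numerator and denominator:

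- With loss: L / n as planned, against (L + k) / (n + k) if retreatment counts as loss.
- Without loss: (n − L) / n as planned, against (n − L) / (n + k).

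Whenever k > 0 and some observed patients have not lost benefit, the planned figures understate loss. For scale, section 4.1 expects about 100 eligible patients and footnote d to Figure JAHO.3.2 randomizes 3:1, so about 100 × 1/4 = 25 go to placebo. Each retreated patient is then about 1/25 = 4 percentage points of that arm.

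**The case against.** The strongest reply is that Table JAHO.4.1 only describes an analysis set. It requires that patients were in fact retreated and tells nobody when to retreat. Footnote g is the only operational trigger in the documents, and step 2 shows that anyone retreated under it also satisfies the table entry. Censoring acts on actual retreatment, not on a SALT threshold. The endpoints are other secondary objectives without multiplicity adjustment, and the final-lock analyses are descriptive. The parenthesis may simply be a shortening of the worsening rule, although the text does not say so.

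Most of this stands. It disposes of two inferences that a reader might draw. One is that the conflict changed who was retreated or censored; no supplied passage shows that SALT above 20 was ever used operationally. The other is that the Retreated Population contains the wrong patients; under footnote g the entry is a looser label for the same patients.

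The reply does not remove the conflict in wording. Footnote g refers to the JAHO(e) protocol for details, and that document is not available here to settle it. Nor does the reply reach step 5: the observed-data proportions lose retreated patients under either trigger.

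**Conclusion.** The inconsistency is real and bounded. The two definitions agree only at a Week 52 SALT of 0 and otherwise differ by the Week 52 score, up to 20 SALT points. A reader might infer a gap of more than 20 points, but the entry limit of SALT 20 rules that out. The documents give no distribution of Week 52 scores or of later worsening, so the number of patients between the two thresholds cannot be stated.

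Under the documented trigger, the conflict by itself changes neither the Retreated Population, nor censoring, nor time to loss. Harm from the wording depends on SALT above 20 having been used to retreat, flag or date loss, which the documents neither show nor exclude. The loss of retreated placebo patients from the observed-data proportions does not depend on that premise. The 4-point scale in step 5 assumes 100 eligible patients and an exact 3:1 split.

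**What to change.** 1. Reconcile Table JAHO.4.1 with Table JAHO.2.1, footnote g, Table JAHO.4.6 and the analysis tables, so that the single definition actually applied appears throughout. This review does not say which clinical rule that should be.
2. In the Table JAHO.4.11 analyses of time to loss and of the proportions with and without loss, count retreatment as loss from the visit at which it occurs, instead of dropping the patient under tertiary censoring. The handling of a retreated patient then no longer depends on the reading. If footnote g was followed, time to loss is unchanged and only the later-visit observed-data proportions move.
3. Report SALT at Week 52 and at retreatment for each patient in the Retreated Population. This shows which trigger operated. If any patient was retreated at 20 points of worsening or less, it also tells the reader that the placebo result includes smaller losses than the endpoint definition.

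The cost is SAP wording, one derivation line and a short listing from data already collected.

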#### **4.2.1.1. Populations for Efficacy Analysis**

The interim analysis at the Decision Point was conducted using the Phase 2, Week 12 IAS population. A second interim analysis was conducted using the Phase 2, Week 36 IAS population.

The efficacy analysis of the primary and key secondary endpoints in the Phase 3 portion will be conducted using the full analysis set (FAS) population at the primary outcome database lock (PO DBL). All other efficacy or health outcome analyses will be conducted in the FAS population or other populations which are dependent on the objective. Analyses assessing the long-term efficacy maintenance or improvement using the randomized withdrawal population, uptitration population or the retreated population will be performed at the Phase 3 F-DBL.

Additional exploratory analyses will be conducted on the FAS population unless, otherwise, stated.

#### **4.2.1.2. Populations for Safety Analysis**

Safety analyses will be conducted using the safety population. Specifically, the safety analysis of Phase 2 portion will use the safety population for the Phase 2 portion whereas the safety analysis of Phase 3 portion will use the safety population for the Phase 3 portion. Safety data will be analyzed for each phase (Phase 2 and Phase 3) by treatment cohort. The treatment cohorts include “as randomized” treatment groups and may include “rescued or switched” to baricitinib 2-mg or 4-mg dose, as appropriate.

For the analysis of safety at the Phase 2 Decision Point interim analysis, data from patients randomized to placebo, baricitinib 1-mg, baricitinib 2-mg, or baricitinib 4-mg and followed up to treatment or dose change or data cut (if no treatment or dose change) of the interim analysis were analyzed.

The safety analysis of the Phase 2, Week 36 interim analysis analyzed safety data up to the data cut-off point, excluding any safety data after the dose change or rescue or beyond Week 52. Refer to [Appendix 2](#) for more details.

At the Phase 3 PO-DBL, the safety data of Phase 3 portion through Week 36 will be analyzed by treatment groups including placebo, baricitinib 2-mg, or baricitinib 4-mg.

At the Week 104 DBL and Week 152 DBL, the safety data will be summarized/analyzed using the Randomized Withdrawal population or the retreated population.

At the F-DBL, the efficacy and safety outcomes will be descriptively summarized using observed data, unless stated otherwise. The safety data will be summarized/analyzed using the safety population unless stated otherwise.

In the rare situation where a patient is Lost to Follow-up at the first postbaseline visit, but some safety data exists (e.g., unscheduled laboratory assessments) after first dose of study drug, a listing of the data or a patient profile will be provided, if requested.

#### **4.2.2. Definition of Baseline and Postbaseline Measures**

The baseline utilized in the efficacy analyses depends on the analysis being performed. The baseline value for the efficacy and health outcome analyses for all populations is defined as the last non-missing measurement on or prior to the date of first study drug administration (expected at Week 0, Visit 2) unless otherwise stated. If a patient is randomized but does not receive study drug, then the date of randomization is used instead of the first dose date. The efficacy and health outcome analyses for the randomized withdrawal population will use the measurement on or immediate prior to the date of Visit 2 (Week 0) or date of visit 11 (Week 52) as baseline as appropriate for the endpoints, unless otherwise stated. The efficacy and health outcome analyses for the retreated population will use the measurement on or prior to the date when patients got retreated.

Baseline for the safety analyses is defined as the last non-missing scheduled (planned) measurement on or prior to the date of first study drug administration for continuous measures by-visit analyses, unless otherwise stated, and all non-missing measurements on or prior to the date of first study drug administration for all other analyses.

Postbaseline measurements are collected after study drug administration through Week 200 (Visit 24) or early discontinuation visit. For data collected in the electronic Clinical Outcomes Assessment (eCOA) tablet (including Patient-Reported Outcomes [PRO] and Clinician-Reported Outcomes [ClinRO]) and related to efficacy assessments, unscheduled postbaseline visits that fall within the visit windows defined by Lilly will be summarized in the by-visit analyses if there is no scheduled visit available. Refer to clinical protocol I4V-MC-JAHO(e) for detail of the visit windows. If there is more than 1 unscheduled visit within the defined visit window and no scheduled visit is available, the unscheduled visit closest to the scheduled visit date will be used. If 2 unscheduled visits of equal distance are available, then the latter of the 2 will be used.

Postbaseline measures for the safety analyses are defined as the non-missing scheduled (planned) measurements after the date of first study drug administration for continuous measures by-visit analyses and all non-missing measurements after the date of first study drug administration for all other analyses.

For the F-DBL safety data will be analyzed on extended safety analysis which includes patients who were continuously treated with baricitinib 2-mg or 4-mg or placebo from baseline and censored in case of dose change. In addition to the above treatment groups, “ALL BARI” will also be included to the summary which includes patients who received at least one dose (2-mg, or 4-mg) of baricitinib at any timepoint during the treatment period.

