the analysis period is defined as first dose date up to min(last dose date, Week 36 visit date, study disposition date). The Week 36 visit date will be imputed if it's missing.

For the long-term safety analysis at the Week 104 DBL, the analysis period defined for the Randomized Withdrawal population is between Week 52 and 104. The analysis period for the retreated population is between the retreatment visit and throughout the min (last dose date+30 days, Week 104 DBL cut-off date).

For the safety analysis at the F-DBL, the analysis period will be Week 0 to 200/248 and will be analyzed based on the safety population. Additionally, exposure data will also be analyzed using randomized withdrawal population and uptitration population.

For selected safety assessments other than events, descriptive statistics may be presented for the last measure observed during post-treatment follow-up (up to 30 days after the last dose of treatment, regardless of study period).

Refer to the compound level safety standards for more details.

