#### **4.14.2. Adverse Events**

Adverse events are recorded in the eCRFs. Each AE will be coded to system organ class (SOC) and preferred term (PT) using the Medical Dictionary for Regulatory Activities (MedDRA) version that is current at the time of database lock. Severity of AEs is recorded as mild, moderate, or severe.

A treatment-emergent adverse event (TEAE) is defined as an event that either first occurred or worsened in severity after the first dose of study treatment and on or prior to the last visit date during the analysis period. The analysis period is defined as the treatment period plus up to 30 days off-drug including follow-up time. For the Weeks 0 to 36 TFLs, the analysis period is defined as first dose date up to min(last dose date+30 days, Week 36 visit date, study disposition date). The Week 36 visit date will be imputed if it's missing. Refer to the compound level safety standards for more details including data imputations.

In general, summaries will include the number of patients in the safety population (N), frequency of patients experiencing the event (n), and the relative frequency (that is, percentage;  $n/N \times 100$ ). For any events that are gender-specific based on the displayed PT, the denominator used to compute the percentage will only include patients from the given gender.

Extended Safety Analysis includes patients who were continuously treated with Baricitinib 2-mg, or 4-mg and Placebo from baseline and censored in case of dose change, or after the permanent study drug discontinuation, whichever occurred earlier. In addition to the above treatment groups "ALL BARI" will also be included to the summary which includes patients who received at least one dose (2-mg, or 4-mg) of BARICITINIB at any time of the treatment period.

In an overview table, the number and percentage of patients in the safety population who experienced death, an SAE, any TEAE, discontinuation from the study due to an AE, permanent discontinuation from study drug due to an AE, or a severe TEAE will be summarized by treatment group.

The number and percentage of patients with TEAEs will be summarized by treatment group in 3 formats:

- by MedDRA PT nested within SOC with decreasing frequency in SOC, and events ordered within each SOC by decreasing frequency in the baricitinib 4-mg dose group or other treatment group in the long-term safety analysis as appropriate.

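### At the Week 104 lock, safety is counted from Week 52 or retreatment but judged against a pre-Week 0 baseline, so abnormalities already present can be labelled as emerging in the later period

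*SAP*

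**What the plan says.** SAP 4.2.2 defines the safety baseline in one sentence with two parts. For continuous by-visit analyses it is "Baseline for the safety analyses is defined as the last non-missing scheduled (planned) measurement on or prior to the date of first study drug" administration, unless otherwise stated. For everything else, which includes shift and treatment-emergent categories, it is "all non-missing measurements on or prior to the date of first study drug administration for all other analyses"; that part carries no exception.

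The same section treats efficacy and health outcomes differently. The Randomized Withdrawal Population uses a value at the "date of Visit 2 (Week 0) or date of visit 11 (Week 52) as baseline as appropriate for the endpoints". For those retreated: "The efficacy and health outcome analyses for the retreated population will use the measurement on or prior to the date when patients got retreated".

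On populations, SAP 4.2.1.2 says: "At the Week 104 DBL and Week 152 DBL, the safety data will be summarized/analyzed using the Randomized Withdrawal population or the retreated population". Table JAHO.4.1 presents withdrawal patients by the arm assigned at Week 52, so there is a withdrawal-placebo column.

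On the period, SAP 4.14 says that for the Week 104 lock "the analysis period defined for the Randomized Withdrawal population is between Week 52 and 104". For the other group: "The analysis period for the retreated population is between the retreatment visit and throughout the min" of last dose plus 30 days and the Week 104 cut-off date. No safety period is given for the Week 152 lock, either there or in 4.17.3.4.

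On adverse events, SAP 4.14.2 defines a treatment-emergent event as one that "either first occurred or worsened in severity after the first dose of study treatment", up to the last visit in the analysis period.

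**The concern.** Entry to randomised withdrawal requires response at Week 52 on the same baricitinib dose since Visit 2 (SAP 4.1). For every patient in the withdrawal-placebo column, the interval between the safety baseline and the start of the counting window was therefore spent assigned to baricitinib. A laboratory or vital-sign value that was normal before Week 0, became abnormal on drug, and is still abnormal after Week 52 satisfies the baseline rule for emergence and falls inside the Week 52 to 104 window. It is then reported as emerging on whatever the patient was assigned at Week 52, including placebo. A Retreated patient can likewise have an abnormality from the first year, or from the placebo interval, counted as emerging on retreatment.

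What is at stake is attribution. A reader takes a period-specific treatment-emergent table to show what started in that period. As written, these tables mix new onset with carry-over and give no means of separating the two.

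**Working it through.** No sample size, power or alpha in the SAP depends on this definition, so there is no planned figure to reproduce. The check is a comparison of sections, then an illustration of size.

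**Comparison of sections (Week 104 lock)**

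| Item | Randomized Withdrawal | Retreated | SAP section |
|---|---|---|---|
| Safety period starts | Week 52 | Retreatment visit | 4.14 |
| Safety baseline | Before first study drug | Before first study drug | 4.2.2 |
| Efficacy baseline | Week 0 or Week 52, as suits the endpoint | On or before retreatment date | 4.2.2 |

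No section gives either population a later safety baseline. The closing paragraph of 4.2.2 on extended safety concerns only the final lock.

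**Size in the placebo column**

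From the SAP: about 100 patients are expected in randomised withdrawal (4.1), allocated 3:1 (footnote d to Figure JAHO.3.2). That gives 100 × 1/4 = 25 on placebo and 75 on baricitinib.

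Assumed, since the documents give no such rates:
- q = share normal before Week 0 but abnormal at Week 52, from 5% to 30%
- s = share of those still abnormal at a later measurement in the period, 1 or 0.5
- r = true new onset in Weeks 52 to 104 among patients normal at Week 52, 5% on placebo

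Apparent treatment-emergent share = q·s + (1 − q)·r. Carried-over patients = 25·q·s. For example, with q = 20% and s = 1: 0.20 + 0.80 × 0.05 = 24.0%, with 25 × 0.20 = 5.0 patients carried over, and 0.20/0.24 = 83% of apparent cases.

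| q | Carried over of 25 (s = 1) | Apparent share (s = 1) | Part that is carry-over | Apparent share (s = 0.5) | Part that is carry-over |
|---|---|---|---|---|---|
| 5% | 1.25 | 9.75% | 51% | 7.25% | 34% |
| 10% | 2.5 | 14.5% | 69% | 9.5% | 53% |
| 20% | 5.0 | 24.0% | 83% | 14.0% | 71% |
| 30% | 7.5 | 33.5% | 90% | 18.5% | 81% |

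With a Week 52 baseline, every row would show 5% of those still at risk.

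**Effect on the arm comparison**

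Assume true new onset of 10% on baricitinib and 5% on placebo (ratio 2.0, difference 5 points), and full persistence on baricitinib. The baricitinib column then shows q + (1 − q) × 0.10.

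| q | Baricitinib | Placebo, all persist | Ratio; difference | Placebo, half persist | Ratio; difference |
|---|---|---|---|---|---|
| 5% | 14.5% | 9.75% | 1.49; 4.75 points | 7.25% | 2.0; 7.25 points |
| 10% | 19.0% | 14.5% | 1.31; 4.5 points | 9.5% | 2.0; 9.5 points |
| 20% | 28.0% | 24.0% | 1.17; 4.0 points | 14.0% | 2.0; 14.0 points |
| 30% | 37.0% | 33.5% | 1.10; 3.5 points | 18.5% | 2.0; 18.5 points |

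If abnormalities persist equally, the contrast shrinks. If half resolve on placebo, the ratio happens to stay at 2.0 while the difference grows. If all resolve on placebo before the next measurement, with q = 20% the table shows 28% against 0.80 × 0.05 = 4%: a ratio of 7.0 and a difference of 24 points.

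**The case against.** The strongest counter-argument is that the rules may be completed elsewhere. SAP 4.14, 4.14.2, 4.14.3 and 4.14.4 refer to the compound level safety standards, and 4.14.3 does so specifically for treatment-emergent low and high laboratory values. A period-specific baseline may be defined there. This stands as a limit on certainty: mislabelling follows from the SAP text but may not occur in practice. It does not cure the text, because 4.2.2 states a baseline for shift and treatment-emergent analyses without exception. If the standards say otherwise, the two conflict.

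A pre-drug reference is also a legitimate descriptive choice, since it shows whether values return to the untreated level after withdrawal. That supports keeping change from Week 0 as a display. It does not support calling an older abnormality emergent in a later period.

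The withdrawal phase was meant to evaluate clinical response after withdrawal and was not sized for a placebo comparison (SAP 4.1). No safety hypothesis rests on these tables, which limits the impact.

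A reader might go further in four ways that the documents do not support:
- **Placebo made to look as toxic as drug.** Carry-over enters both arms, and randomisation balances it in expectation at Week 52. Dilution towards no difference requires abnormalities to persist about equally off drug; with faster resolution on placebo the difference is exaggerated.
- **The same fault shown at Week 152.** The SAP names the populations for that lock but no safety period, so this is a gap, not a demonstrated mismatch.
- **Adverse events certainly miscounted.** The first-dose wording has no lower bound at Week 52, but restricting onset to the analysis period would exclude earlier events. The text allows either reading.
- **Loss of precision in safety ANCOVA.** SAP 4.2.3 describes that model generally, but 4.11.5 makes analyses beyond Week 36 descriptive unless otherwise stated, and no section schedules it for these populations at this lock.

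**Conclusion.** The baseline rule is wrong as written for the period-specific categorical laboratory and vital-sign tables at the Week 104 lock. The window opens at Week 52 or retreatment, the reference stays before Week 0, and the re-baselining that 4.2.2 provides for efficacy has no safety counterpart. Abnormalities that arose in the first year on baricitinib and persist are therefore attributed to the later period, in both withdrawal arms and in the Retreated Population.

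Under the assumed 5% to 30% prevalence at Week 52 with full persistence, 1.25 to 7.5 of about 25 withdrawal-placebo patients would be mislabelled. With 5% true new onset, that is roughly half to nine tenths of the apparent placebo cases. These rates are illustrative; only the expected 100 patients and the 3:1 ratio come from the SAP. The direction of bias in the arm comparison cannot be stated without knowing resolution off drug.

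For adverse events the defect is an ambiguity that needs a stated rule. The final-lock safety analysis, from Week 0 to Week 200/248 on the safety population, does not have this mismatch.

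**What to change.** In SAP 4.2.2 and 4.14.2, state for period-specific safety tables:
- **Randomized Withdrawal Population:** the baseline and treatment-emergent reference is the last value on or before the first dose after Week 52 randomisation.
- **Retreated Population:** it is the last value on or before the first retreatment dose.
- **Treatment-emergent:** only what first occurs or worsens after that dose. This also settles events that began before Week 52.
- **Already ongoing:** adverse events and abnormalities present at the new baseline are listed separately, so nothing is lost from view.
- **Week 0 reference:** change from Week 0 may be kept as an additional, labelled display.

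State the safety analysis period for the Week 152 lock and apply the same rule. Check the wording against the compound level safety standards and say which governs if they differ.

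The cost is a few sentences and a re-run of the affected tables on existing data. Treatment-emergent counts in those tables would fall where there is carry-over, and denominators for categorical tables would be patients without the abnormality at the new baseline.
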